### Stratification

A shift table on randomized patients will describe the strata recorded in IVRS (no additional LMT, or intent to initiate fenofibrate, ezetimibe, omega-3 fatty acids, or nicotinic acid) and the actual LMT received recorded in the e-CRF on the UC medication page. A listing of patients with discrepancies between strata will be provided.

#### 2.2.1 Randomization and drug dispensing irregularities

Randomization and drug-dispensing irregularities occur whenever:

1. A randomization is not in accordance with the protocol-defined randomization method, such as a) an ineligible patient is randomized, b) a patient is randomized based on an incorrect stratum, c) a patient is randomized twice, or d) in a dynamic randomization scheme the treatment assignment is, in fact, not random, due to a computer program error.

OR

2. A patient is dispensed an alirocumab kit/ usual care package (e.g., blister packs, pill container) not allocated by the protocol-defined randomization, such as a) a patient at any time in the study is dispensed a different treatment kit/package than as randomized (which

26-Apr-2017

Version number: Final

26-Apr-2017

may or may not contain the correct-as-randomized IMP), or b) a nonrandomized patient is treated with IMP reserved for randomized patients.

Randomization and drug-dispensing irregularities will be monitored throughout the study and reviewed on an ongoing basis. Randomization irregularities are recorded in the IVRS/IWRS. Drug dispensing irregularities come from IVRS/IWRS only for the alirocumab arm, as the process of drug supply for usual care is not handled by IVRS/IWRS and is site-specific. Therefore drug dispensing irregularities presented in this section will only concern the alirocumab arm. The corresponding information for usual care would be found in the CSR as qualitative deviations in the specific section.

Randomization and drug-dispensing irregularities to be prospectively identified include but are not limited to:

Randomization irregularities (both treatment arms)	Drug dispensation irregularities (alirocumab)	
Randomization by error	Alirocumab kit dispensation without IVRS transaction	
Patient randomized twice	Erroneous alirocumab kit dispensation	
Stratification error	Alirocumab kit not available	
	An alirocumab kit allocated at Day 1 or any unscheduled replacement before Week 12 is administered to the patient after his up-titration visit (Week 12)	

All randomization and drug-dispensing irregularities will be documented in the clinical study report. If the number of irregularities is large enough to make a tabular summary useful, the irregularities will be categorized and summarized among randomized patients (number and percentages). Non-randomized, treated patients will be described separately. A listing of randomization and drug allocation irregularities as well as a listing of patients randomized twice (or more) or treated but not randomized will be produced.

A listing of patients with treatment group as randomized different than treatment group as treated will be produced.

# 2.3 ANALYSIS POPULATIONS

Patients treated without or before being randomized will not be considered randomized and will not be included in any analysis population. The safety experience of these patients will be reported separately.

The randomized population includes all randomized patients as defined in Section 2.2.

For any patient randomized more than once, only the data associated with the first randomization will be used in any analysis population. The safety experience associated with any later randomization will be assessed separately.

## 2.3.1 Efficacy populations

The primary efficacy analysis population will be the ITT population.

## 2.3.1.1 Intent-to-treat population

The ITT population is defined as all randomized patients who have an evaluable primary efficacy endpoint defined as:

- Baseline non-HDL-C value available;
- At least one non-HDL-C value available within one of the analysis windows up to Week 24.

Patients in the ITT population will be analyzed according to the treatment group allocated by randomization.

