	add no additional LMT on top of the maximum dose/regimen of statin that is tolerated by the patient or to start one of the following treatments: ezetimibe, fenofibrate, omega-3 fatty acids or nicotinic acid. All patients, regardless of the usual care option that has been selected, should continue on the maximum dose/regimen of statin (non-IMP) that is tolerated by the patient.
	The following drugs are identified as IMP:
Formulation:	Ezetimibe, or
	Nicotinic acid, or
	Fenofibrate, or
	Omega-3 fatty acids
Route(s) of administration:	Oral
Dose regimen:	As applicable and in accordance with Investigator prescription/local labeling.
Noninvestigational medicinal product(s) (if applicable)  Formulation:	No non-investigational products will be provided by the Sponsor. The following non-investigational products may be taken by the patient, as applicable, and in accordance with the eligibility criteria: statins (HMG CoA reductase inhibitors).
Route(s) of administration:	As applicable and in accordance with local labeling.
Dose regimen:	As applicable and in accordance with local labeling.
ENDPOINT(S)	Primary endpoint:
	
 
Percent change in non-HDL-C from baseline to Week 24 in the intent-to-treat (ITT) population, using all non-HDL-C values regardless of adherence to treatment (ITT estimand).
 

	Key Secondary Efficacy endpoints (ITT estimand)
	Percent change in measured LDL-C from baseline to Week 24.
	Percent change in non-HDL-C from baseline to Week 12.
	Percent change in measured LDL-C from baseline to Week 12.
	Percent change in Apo B from baseline to Week 24.
	Percent change in Total-C from baseline to Week 24.
	Percent change in Lp(a) from baseline to Week 24.
	Percent change in TGs from baseline to Week 24.
	Percent change in HDL-C from baseline to Week 24.
	
 
Percent change in LDL particle number from baseline to Week 24.
 
Diabetes-related endpoints (ITT estimand)
 

	
 
Absolute change in HbA1c from baseline to Weeks 12 and 24.
 
Absolute change in fasting plasma glucose (FPG) from baseline to
 

	

Weeks 12 and 24.

Absolute change in number of glucose-lowering treatments from

	baseline to Weeks 12 and 24.
	Safety endpoints
	
 
Treatment emergent adverse events (TEAEs), adverse events of special interest (AESIs), product complaints, laboratory data
 

(including microalbuminuria), vital signs (including change in body weight and BMI).

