## 11.3.1.1 Intent-to-treat population

The ITT population is defined as all randomized patients who have an evaluable primary efficacy endpoint.

The primary efficacy endpoint is evaluable when the two following conditions are met:

- The baseline non-HDL-C value is available
- At least one non-HDL-C value is available within one of the analysis windows up to Week 24.

Patients in the ITT population will be analyzed according to the treatment group allocated by randomization.

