### 2.1.3.1 Primary efficacy endpoint

The primary efficacy endpoint is the percent change in non-HDL-C from baseline (see definition of baseline in Section 2.1) to Week 24 in the intent-to-treat (ITT) population.

Non-HDL-C is defined as Total-C minus HDL-C.

The percent change is defined as: 100 x (non-HDL-C value at Week 24 - non-HDL-C value at baseline) / non-HDL-C value at baseline.

26-Apr-2017

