#### 2.4.4 Analyses of efficacy endpoints

For statistics where international and conventional units do not impact the results (e.g., means and least square (LS) means for percent changes from baseline, p-values for both percent and absolute changes from baseline, rates of patients below a threshold), derivations will be performed and statistical models will be run using conventional units. For other statistics (e.g., descriptive statistics at baseline and over time, absolute changes from baseline), derivations will be done with both international and conventional units.

All the efficacy endpoints (primary, key secondary and other efficacy endpoints) will be analyzed in the ITT population for the overall comparison (alirocumab versus usual care) and for patients intended to receive fenofibrate in order to compare the efficacy of alirocumab versus fenofibrate. However no subgroup analysis will be performed in the fenofibrate stratum.

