## Sensitivity to randomization strata

In order to assess the robustness of the primary analysis to randomization stratum mistakes (i.e., the stratum recorded in IVRS differs from the actual one), the MMRM model will be re-run including the actual stratum as per the e-CRF instead of the stratum recorded in IVRS. The actual stratum as per the e-CRF is defined, for the patients randomized to usual care only, as the actual usual care treatment taken for the longer time. In case no additional LMT is recorded using e-CRF page "Usual Care Medication for Lipid Modification therapy", the actual stratum will be assigned to "no intent to prescribe an additional LMT".

Sensitivity to handling of missing data - Pattern mixture model

In order to assess the robustness of the primary efficacy analysis with regards to handling of missing data, a sensitivity analysis will be conducted based on a pattern-mixture model approach.

Multiple imputation will be used with different imputation strategies applied to non-HDL-C values missing during the on-treatment period (as defined below)

- Patients randomized to alirocumab would continue to show benefit from treatment similar to that observed at the scheduled time point within 21 days of their last dose of open-label alirocumab (on-treatment period). Therefore, non-HDL-C values missing during the ontreatment period (e.g., samples obtained outside the specified window, no blood sample available although visit was performed, etc) should be considered as "Missing At Random" and imputed using a model based on other on-treatment measurements, gender, age and BMI;
- Patients randomized to usual care with additional LMT would continue to show benefit from treatment similar to that observed at the scheduled time point within 3 days of their last dose of LMT. Therefore, non-HDL-C values missing during the on-treatment period (e.g., samples obtained outside the specified window, no blood sample available although visit was performed, etc) should be considered as "Missing At Random" and imputed using a model based on other on-treatment measurements, gender, age and BMI;
- Patients, randomized to usual care and for whom the Investigator has not prescribed an additional LMT, would tend to have non-HDL-C values similar to baseline. Therefore, non-HDL-C values missing after randomization should be imputed based on patient's own baseline value;

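### The pattern-mixture analysis inherits an ITT set that omits randomized patients with no windowed post-baseline non-HDL-C value, although its own rules could use most of them

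*SAP*

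**What the plan says.** SAP 2.3.1.1 sets two conditions for the ITT population: "Baseline non-HDL-C value available" and "At least one non-HDL-C value available within one of the analysis windows up to Week 24". Protocol 11.3.1.1 agrees: "The ITT population is defined as all randomized patients who have an evaluable primary efficacy endpoint". The windows in SAP 2.5.3, Table 2, start at Day 15 and include none for baseline, so the second condition requires a post-baseline value. Under Protocol 1.2 the first scheduled post-baseline lipid sample is at Week 8; Week 4 is a telephone contact.

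The primary endpoint is the percent change "to Week 24 in the intent-to-treat (ITT) population" (SAP 2.1.3.1), and SAP 2.4.4 adds: "All the efficacy endpoints (primary, key secondary and other efficacy endpoints) will be analyzed in the ITT population". The MMRM uses Week 8 to Week 24 values. SAP 2.4.4.1.1 acknowledges that missingness may be non-ignorable and points to the pattern-mixture model in 2.4.4.1.3, whose stated purpose is: "In order to assess the robustness of the primary efficacy analysis with regards to handling of missing data". That text names no population. Its imputation rules depend on treatment status:

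- Usual care without an added lipid therapy: "non-HDL-C values missing after randomization should be imputed based on patient's own baseline value".
- Any patient after the on-treatment period (21 days past the last alirocumab dose, 3 days past the last dose of an added therapy): own baseline.
- Values missing while on alirocumab or an added therapy: imputed as missing at random.

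Patients left out of the ITT population are listed, and population sizes are summarized by treatment group (SAP 2.2). Protocol 10.3.5 leaves it to the SAP to say how the primary endpoint is handled after loss to follow-up.

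**The concern.** A missing-data sensitivity analysis should cover the patients for whom the missing-data assumption matters most. Here, those with every windowed value missing are removed before the check begins. Allocation is known to patient and investigator, and no lipid sample is scheduled for eight weeks, so loss in that interval could differ between arms for reasons related to treatment. The MMRM cannot learn from such patients. The pattern-mixture model can, since two of its three rules need only a baseline value. At stake is whether the one analysis meant to probe non-ignorable missingness can show the effect of this exclusion. The other two sensitivity analyses in SAP 2.4.4.1.3 (treatment change, actual stratum) re-run the primary model and do not restore these patients.

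**Working it through.** The plan gives no figure to reproduce: effect size, SD and dropout rate are not in the public text. The check is structural, followed by an illustration on assumed inputs.

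**1. Who is excluded.** Table 2 has windows at Days 15-42, 43-70, 71-98, 127-154 and 155-182. (In the alirocumab arm the third may end earlier, at the first injection from the Week 12 kit.) No window covers Days 2-14 or Days 99-126. Excluded are patients with no baseline value, patients with no post-baseline value, and patients whose only post-baseline values fall in those gaps. One route is an early end-of-treatment sample (Protocol 10.3.4) taken before Day 15, with no later sample.

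**2. Which imputation rule would apply.** Take a patient lost by Day 70, the end of the Week 8 window. SAP 2.5.2 imputes a missing last-dose date no later than last contact. The on-treatment period for alirocumab then ends by Day 70 + 21 = Day 91, before the Week 24 window opens at Day 155. The missing Week 24 value therefore falls under the own-baseline rule. For an added usual-care therapy the limit is Day 73. Usual care without an added therapy gets own baseline in any case. The exceptions are patients still on treatment at Week 24 without a windowed sample, whose values are imputed as missing at random, and patients never treated, for whom the text gives no explicit rule.

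**3. Size, on assumed inputs.** Let the mean changes be m1 = -35% (alirocumab) and m0 = -5% (usual care), so that the ITT difference is -30 points. Let xa and xu be the shares of each randomized arm added back at own baseline, that is, at 0% change. Then

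D = m1(1 - xa) - m0(1 - xu) = -35(1 - xa) + 5(1 - xu),

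and the shift is D - (-30) = 35xa - 5xu. Patient counts use the planned 280 and 140.

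| xa | xu | Patients | D | Shift |
|---|---|---|---|---|
| 2% | 2% | 5.6 + 2.8 | -29.40 | +0.60 |
| 2% | 5% | 5.6 + 7 | -29.55 | +0.45 |
| 5% | 2% | 14 + 2.8 | -28.35 | +1.65 |
| 5% | 5% | 14 + 7 | -28.50 | +1.50 |
| 10% | 0% | 28 + 0 | -26.50 | +3.50 |
| 0% | 5% | 0 + 7 | -30.25 | -0.25 |

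The shift is away from the null whenever 5xu > 35xa, that is, xu > 7xa.

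With smaller assumed changes (-20% and -10%, difference -10), 5% in both arms gives -20(0.95) + 10(0.95) = -9.5; 10% in alirocumab only gives -18 + 10 = -8.0; 5% in usual care only gives -20 + 9.5 = -10.5.

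**The case against.** Several points against the concern have force.

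- **The tie to the ITT set is inferred.** The pattern-mixture text names no population. The link comes from SAP 2.1.3.1, SAP 2.4.4 and the stated purpose of checking the primary analysis. This stands as a caution, but nothing in the documents points to another set.
- **Early treatment stop is not the same as exclusion.** Patients who stop should continue all visits and, if possible, be sampled within 5 days (Protocol 10.3.4, which does not apply to usual care without an added therapy). Unscheduled values count, and a sample from Day 15 falls in the Week 4 window. Exclusion generally needs loss before any windowed sample. This stands and limits the likely number.
- **The check already goes beyond the MMRM data.** A patient whose only value is in the Week 4 window is in the ITT set, adds no outcome to the MMRM, and would have Week 24 imputed in the pattern-mixture analysis. This is correct, but it does not help patients with no windowed value.
- **There is some transparency.** Exclusions are listed, population sizes are given by arm, and baseline tables are repeated if the ITT and randomized sizes differ by more than 10% in any arm (SAP 2.4.1). A reader could do the bounding arithmetic, but the plan does not.

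Two stronger readings are tempting. A reader might infer that the exclusion always favours alirocumab. The formula does not support that: loss concentrated in usual care moves the difference the other way. A reader might also infer that the plan contradicts its own estimand, since the protocol summary defines the endpoint "using all non-HDL-C values regardless of adherence to treatment (ITT estimand". That phrase governs which values are used, and the same sentence places the endpoint in the ITT population as defined, so there is no contradiction.

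**Conclusion.** The point holds for the pattern-mixture analysis only. That check, the plan's sole not-missing-at-random analysis, omits randomized patients whom most of its own rules could handle. A reader might go further and conclude that the primary result is biased by the choice of set. The documents do not support that as a criticism of the MMRM, since adding patients with no outcome value would leave its estimate and test unchanged.

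On the assumed -35% and -5%, the shift is about 0.5 to 1.7 points towards the null for 2% to 5% excluded in both arms. It reaches 3.5 points for 10% in alirocumab only and reverses for usual care only. These figures rest on assumed effects and exclusion rates, on a zero mean change for everyone added back, and on a simple difference of means without covariate adjustment. Patients imputed as missing at random would add little shift, so xa and xu are the shares given the baseline value. A shift of this size is unlikely to overturn a large effect. The change is still worth making, because it is cheap and the present check cannot show what the exclusion does.

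**What to change.** In SAP 2.4.4.1.3, state that the pattern-mixture analysis is run on all randomized patients with a baseline non-HDL-C value, and apply the existing rules by status:

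- own baseline for values missing after the on-treatment period and for usual care without an added therapy;
- own baseline also for patients never treated, stated explicitly because the present text does not cover them;
- the existing missing-at-random imputation for values missing while on treatment.

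Report the number excluded from the ITT population by arm and by randomization stratum. The stratum breakdown matters because the fenofibrate comparison is tested separately at 0.025. Keep the MMRM and its population as primary.

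The cost is a few lines of SAP text, a slightly larger input data set, and a sensitivity estimate that will probably be slightly smaller. Data collection, alpha and the primary test do not change.

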# 2.3.2 Safety population

The safety population considered for safety analyses will be the randomized population who did actually receive at least one dose or part of a dose of the open-label alirocumab and all patients randomized to usual care.

Patients will be analyzed according to the treatment actually received (usual care or alirocumab).

The safety analysis will focus on the TEAE period defined in Section 2.1.4.

In addition:

- Non-randomized but treated patients or patients treated before the randomization will not be part of the safety population, but their safety data will be presented separately;
- Randomized patients for whom it is unclear whether they took the study medication will be included in the safety population as randomized;
- For patients receiving more than one study treatment during the trial, the treatment group allocation for as-treated analysis will be the one to which the patient was treated with the longest duration.

# 2.3.3 Anti-alirocumab antibody population

The ADA analysis will be performed on safety population with a blood sample for antibodies at Week 0 (baseline) and at least one evaluable blood sample for antibodies post-baseline.

Property of the Sanofi Group - strictly confidential

# 2.3.5 Proprotein convertase subtilisin kexin type 9 population

The PCSK9 analysis will be performed on all randomized patients with a baseline sample of PCSK9 at Week 0 (baseline) and at least one evaluable blood sample for PCSK9 level post-baseline (Week 12 and/or Week 24).

#### 2.4 STATISTICAL METHODS

## 2.4.1 Demographic and baseline characteristics

Parameters described in Section 2.1.1 will be summarized by treatment group and overall using descriptive statistics. Continuous data will be summarized using the number of available data, mean, SD, median, first quartile (Q1) and third quartile (Q3), minimum, and maximum for each treatment group. Categorical and ordinal data will be summarized using the number of non-missing data and the number and percentage of patients (the denominator being the number of non-missing values) in each treatment group and overall.

P-values on demographic and baseline characteristic data will not be calculated.

Parameters will be summarized on the randomized population in the treatment group to which they were randomized (as per IVRS). Analyses will be repeated for the ITT population if the size of the ITT population is different (>10%) from the size of the randomized population in any treatment group. Similarly, parameters will be repeated in the safety population if the randomized population and the safety population have different size (>10%) in any of the treatment groups (defined by the actually received treatment group).

For the randomized population, parameters will also be summarized within each randomization stratum as per IVRS (for strata with at least 10% of patients).

#### 2.4.1.1 Medical history

Patients with clinical ASCVD, defined as per protocol and as per the 2013 AHA/ACC guidelines (see Section 2.1.1) will be described using the number (%) of patients in each ASCVD component.

For the patients with no clinical ASCVD as per protocol, the following will be tabulated:

- The number (%) of patients having additional CV risk factors as defined in Section 2.1.1 (number (%) for each CV risk factor)
- The number (%) of patients with target organ damage due to diabetes (microalbuminuria, macroalbuminuria, retinopathy (pre-proliferative or proliferative) and/or CKD)
- The number (%) of patients with at least one additional CV risk factor (see Section 2.1.1):

- o 1 CV risk factor
- o 2 CV risk factors
- ≥3 CV risk factors

Other CV medical history, other allergic medical history and all other relevant medical/surgical history will be presented by primary SOC and HLT. The table will be sorted by SOC internationally agreed order and decreasing frequency of HLT based on the overall incidence across treatment groups.

# 2.4.1.2 Correlation analysis at baseline

Linear regressions adjusted on sex, randomization strata and age (as continuous covariate) will be performed to analyze correlation between:

- baseline non-HDL-C and HbA1c,
- baseline non-HDL-C and total PCSK9,
- baseline non-HDL-C and free PCSK9,
- baseline total PCSK9 and HbA1c
- baseline free PCSK9 and HbA1c

if the variables (non-HDL-C, HbA1c and PSCK9 levels) are not normally distributed, they will be log-transformed.

Five scatter plots will be produced with regression lines plotted overall and by randomization strata (only for strata with at least 10% of patients).

